An adverse event is defined as any untoward medical occurrence in a participant which does not necessarily have a causal relationship with the study treatment. All adverse events will be collected after the participant has provided consent and enrolled into the study. If subject experiences an adverse event after the informed consent document is signed (entry) but the participant has not started to receive study intervention, the event will be reported as not related to stimulus control therapy.

All adverse events occurring after entry into the study and until hospital discharge will be recorded.

If treatment is discontinued as a result of an adverse event, study personnel will document the circumstances and data leading to discontinuation of treatment.

The study will monitor for potential adverse effects at each treatment session or workshop.

Adverse events reported spontaneously or in response to open-ended questions asked routinely at each visit (by the study coordinator, psychiatrist or nurse) will be recorded with a medical evaluation of severity and causality and coded using the Medical Dictionary for Regulatory Activities (MEDDRA), Preferred Terms will be reported.

Serious Adverse Event Reporting

A Serious Adverse Event (SAE) is defined as any untoward medical occurrence that results in the following: death, is life-threatening (that is, imminent risk of death), requires medical inpatient hospitalisation or prolongation of existing hospitalisation, persistent or significant disability/incapacity, condition requiring unnecessary medical or surgical intervention. An SAE can also be a significant hazard as determined by the trial investigators. Serious adverse events occurring after a participant has left the study will not be reported unless the investigators feels that the event may have been caused by sleep consolidation therapy or a protocol procedure. Investigators will determine relatedness of an event based on a temporal relationship to the treatment, as well as whether the event is unexpected or unexplained given the participant's clinical course, previous medical conditions, and any concomitant medications

An SAE also includes adverse event that might have led to death or a serious deterioration in health had suitable action or intervention not taken place:

- 1) A malfunction of device such that it has to be modified or temporarily/permanently taken out of service
- 2) A factor found on examination of the device (a deterioration in characteristics or performance)

De-identified Serious Adverse Event Reports will be completed as required throughout the study period and sent the ethic committee.

Early Termination

Possible circumstances for early termination of the study include:

1. Early termination initiated by patient due to side-effects, change-of-mind, intolerability, or the perception that their sleep have improved sufficiently such that they no longer require participation in the program.
2. Loss of capacity to consent due to deterioration or variation in mental state
3. Loss of ability to participate due to deterioration or variation in mental state
4. Medical admission of patient due to an acute medical illness whilst inpatient at PMBC
5. Transfer of patient to a different facility.

The study coordinator will be responsible for correspondence with HREC.

Investigators involved in implementing the Sleep Program clinically, can receive formal notification of termination from the participant by verbal or written form. They may receive notice of termination through a delegate (such as the participant's nurse or medical officer responsible). The investigator will need to formally inform the Study Coordinator in written form.

The Study Coordinator will then be required to document termination in digital study data for this participant – whose data will be separated from overall data pool. Early termination data will be kept for discussion purposes but will be excluded in results and statistical analyses.

The Study Coordinator will be responsible for informing the

(who is responsible for what aspect in the process of terminating the study (informing participants, correspondence to HREC, compiling a final study report, unbinding if applicable)).

BLINDING AND UNBLINDING

- a) Blinding (Masking): This trial is an open-label with no attempt at masking
- b) Emergency unblinding: not applicable

STATISTICAL CONSIDERATIONS

Sample Size or Power Calculation

The pilot study will determine the sample size. Power calculation will be the minimum number of samples required to provide adequate power for the primary outcome. (Actigraphic changes in sleep duration)

Statistical Analysis Plan

Given the pilot study nature we will describe the sample, and the outcomes using but only use analytical techniques to estimate potential effects using difference of means within person measures in SPSS. The pilot study is unlikely to generate sufficient data points for bivariate or multivariate regression modelling.

DATA SECURITY, STORAGE AND ARCHIVING OF STUDY DOCUMENTS

Data Safety and Storage

There are two forms of data collected in pilot study: digital data, and physical data handwritten on paper forms.

Digital Data

Patient name, MRN and date of birth are linked to a Participant ID number. This is kept on an Excel spreadsheet, which is password protected on a single desktop issued by the Sydney Local Health District. The computer will be kept on-site only, in the secured, staff-only section of PMBC, which is accessible via swipe card only. The patient data spreadsheet can only be accessible within a Sydney LHD premises which has access to the SLHD intranet. Back-up copy of this spreadsheet is kept within the Sydney LHD ICT infrastructure.

De-identified digital data includes all data that are entered digitally, and are only identifiable through Participant ID. This includes any digitised data from physical forms, actigraphy data, aggregate length-of-stay data, and so on. Computers with access to these files that are password-protected and individualised for the investigator.

For security, a complete back-up of the data will be kept on a separate, secure Sydney LHD laptop, and is performed on a daily basis. Periodic data analysis files will also be backed-up and kept. Primary access to the Sydney LHD computing facilities will be through physical access onsite and through the intranet. Security will be enforced through restricted, swipe-card physical access, passwords and different levels will be assigned to groups and individuals.

Physical Data

Physical data includes the following; patient-completed self-assessment forms (PSQI, sleep diary, Visual scales), equipment check-in and check-out equipment logs. These are identifiable to patient with *only* the Participant ID.

Any original study forms will be entered onto the computer as de-identified patient data. The original forms are then kept on file at the [name] Centre. Participant files will be stored in numerical order and in a secure cabinet within an office in the staff-only section (swipe-card access) of the PMBC. All participant files will be maintained for 15 years after the completion of the study.

Dissemination of the outcomes of the project

Sleep Actigraphy data will be identifiable only by Participant ID and will be given directly to the patient and not to any third party. This is part of the feed-back and discussion process in the Sleep Program.

The overall outcomes of the project will be disseminated in a confidential envelope with generalised outcomes (that are not identifiable to any original participant) and sent to the patient or given to the patient (if they are still inpatient in a lower acuity ward).

Findings of this pilot study will likely be submitted for publication in relevant scientific journals.

REFERENCES

- Ancoli-Israel, Sonia, et al. "The Role of Actigraphy in the Study of Sleep and Circadian Rhythms." *Sleep*, vol. 26, no. 3, 2003, pp. 342–392., doi:10.1093/sleep/26.3.342.
- Benca, R. M., Obermeyer, W. H., Thisted, R. A., & Gillin, J. C. (1992). Sleep and psychiatric disorders: a meta-analysis. *Archives of general psychiatry*, 49(8), 651-668.
- Cauter, Eve Van. "Circadian and Sleep-Related Endocrine Rhythms in Schizophrenia." *Archives of General Psychiatry*, vol. 48, no. 4, Jan. 1991, p. 348., doi:10.1001/archpsyc.1991.01810280064009
- Cole, R. et al (1992). Automatic sleep/wake identification from wrist activity. *Sleep*, 15, 461.
- Czeisler, C. A., Weitzman, E. D., Moore-Ede, M. C., Zimmerman, J. C., & Knauer, R. S. (1980). Human sleep: its duration and organization depend on its circadian phase. *Science*, 210 (4475), 1264-1267.

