Health
Sydney
Local Health District

PMBC Sleep Program

PROTOCOL NUMBER: VERSION 1.0 (APRIL 2018)

ADMINISTRATIVE INFORMATION

DATA CATEGORY	INFORMATION
Scientific Title	A pilot evaluation of sleep program to improve sleep quality in male psychiatric HDU inpatients
Public Title	PMBC sleep program
Date of Registration	TBC
Primary registry and trial identification number	TBC
Date of Registration in primary registry	TBC
Secondary identification numbers	TBC
Source of monetary or material support	Fully funded by the Sydney Local Health District (\$50,000)
Primary Sponsor	Sydney Local Health District
Contact for public queries	[name] [name], [contact]
Contact for scientific queries	[name] [name], [contact]
Countries of recruitment	Australia
Health condition(s) or problem(s) studied	Inpatient male HDU psychiatric patients of all diagnoses
Intervention(s)	Ward-based initiatives and activity groups
Comparator	Routine male inpatient psychiatric HDU patients' length of stay with and without therapy; previous admissions
Inclusion criteria	Males aged 18+ years. Able to give informed written consent. Literacy in English. Inpatient at PMBC psychiatric Male High Dependency Unit (HDU).
Exclusion criteria	Current substance dependence. Severely unwell such that not able to give consent or tolerating participation in group sessions. Severe cognitive impairment or thought disorder. Not

	proficient in English. Recent transmeridian (>2 time zones) travel (within last 1 month).
Study type	Interventional; Allocation: nonrandomized; Masking: none (open label trial)
Primary Purpose	Pilot Study, Feasibility Study
Date of first enrolment	May 2018
Target sample size	N/A (Pilot study, rolling recruitment)
Recruitment status	Recruitment not yet commenced.
Primary outcomes	Actigraphic changes in sleep duration (Respironics Actigraphy data)
Key secondary outcomes	
Sleep quality (weekly Visual Analogue Scale (VAS) and Pittsburgh Sleep Quality Index measured at start and end of study)
 
Self-report duration
 
Length of stay in HDU
 
Use of as needed (PRN) sedatives for sleep
 
Sleep efficiency (actigraphy)
 
Engagement in group
 
Autonomy
 
Participant satisfaction

Protocol Version:	Version 1.0, April 2018
Revision Chronology	Version 1.0, April 2018: Original.
Protocol Amendment Number	0
Authors	[name] BE(Hons) BCom MBBS, [name] BPsych(Hons), [name] MBBS PhD

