In conclusion, scientific research suggests that in the clinical setting, actigraphy is reliable for evaluating sleep patterns in patients with insomnia, for studying the effect of treatments designed to improve sleep, in the diagnosis of circadian rhythm disorders (including shift work), and in evaluating sleep in individuals who are less likely to tolerate PSG, such as inpatient psychiatric patients. While actigraphy has been used in research studies for many years, it is only recently that the methodological issues have been systematically addressed in clinical research and practice. With those issues addressed, the use of actigraphy is now being applied to clinical practice. (Ancoli-Israel et al, 2003).

STUDY OBJECTIVES

Primary Objective

To evaluate the effect of the Sleep Program on duration of admission in HDU (compared to controls) and sleep duration (Actigraphy data), in male psychiatric HDU inpatient participants.

Secondary objectives

1. Sleep quality - improvement in the Pittsburgh Sleep Quality Index
2. Sleep efficiency- percentage time in bed vs percentage time asleep
3. To test the engagement (tolerability and practicality) with a structured Stimulus Control Therapy Program
4. Impact on use of as needed (PRN) hypnotics
5. To describe the characteristic of sleep, activity and light exposure of patients in a high dependency psychiatric unit using wrist actigraphy.

Hypotheses

- We hypothesise that a structured stimulus control program for sleep will shorten duration of admission at psychiatric HDU.
- There will be an improvement in the sleep duration and efficiency
- There will be an improvement in the quality of sleep via a reduction of the self-rated Pittsburgh Sleep Quality Index score, measured at the beginning and end of the study.
- Participants in the Bright Light Study will engage in a structured stimulus control therapy program and it will be well-tolerated.

STUDY DESIGN

Design, Study Groups, Number of Participants

This is a pilot study for a complex intervention and we do not know the effect of variance. We seek to test our methodology, exterminate recruitment and retention rates, feasibility and finally, determine the sample size. We also seek to highlight any issues with acceptability, compliance, and delivery of our interventions.

Number of centres

Single-centre, at [name] Centre, male High Dependency (psychiatric) Unit

Duration

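### HDU length of stay is in the primary objective but listed as a secondary outcome, and the stated within-person analysis cannot compare it with routine HDU patients

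*Protocol*

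**What the plan says.** Under Study Objectives, the Protocol's Primary Objective joins two endpoints: "To evaluate the effect of the Sleep Program on duration of admission in HDU (compared to controls) and sleep duration (Actigraphy data". The first entry under Hypotheses is "We hypothesise that a structured stimulus control program for sleep will shorten duration of admission at psychiatric HDU". Length of stay does not appear among the five secondary objectives.

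The Administrative Information table gives one primary outcome, "Actigraphic changes in sleep duration (Respironics Actigraphy data", and places "Length of stay in HDU" under key secondary outcomes. Its Comparator entry reads "Routine male inpatient psychiatric HDU patients' length of stay with and without therapy; previous admissions", and its Study type entry reads "Allocation: nonrandomized; Masking: none (open label trial".

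Sample Size or Power Calculation refers to "adequate power for the primary outcome. (Actigraphic changes in sleep duration".

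The Statistical Analysis Plan section of the Protocol says that the sample and the outcomes will be described. For effects, it says that the study will "only use analytical techniques to estimate potential effects using difference of means within person measures in SPSS". It adds that there will probably be too few data points for regression, even with a single predictor.

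**The concern.** Two things do not fit together.

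First, the Protocol gives length of stay two ranks. A reader of the objectives and hypotheses would treat a shorter HDU stay as a main question of the study. A reader of the Administrative Information table or the sample size section would not.

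Second, the objective asks for a contrast between patients, namely participants against controls, while the method stated for estimating effects works within a person. If both stay as they are, the report owes its readers an effect on length of stay that the stated method does not supply for the comparator named first. There would then be pressure to fill the gap with an unplanned comparison in a non-randomised, open-label study.

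**Working it through.** No arithmetic applies. The Protocol states no target sample size, significance level, power, effect size or standard deviation. The check is a comparison of the relevant places in the text.

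**Step 1: rank of each endpoint.**

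- Study Objectives, Primary Objective: length of stay against controls and actigraphic sleep duration, both primary.
- Study Objectives, Hypotheses: shorter HDU stay comes first; sleep duration and efficiency come second.
- Study Objectives, Secondary objectives: length of stay is absent.
- Administrative Information: sleep duration is the only primary outcome; length of stay is a key secondary outcome.
- Sample Size or Power Calculation: sleep duration is the only primary outcome.

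Sleep duration is primary wherever a primary endpoint is named. Length of stay is primary in the objectives and secondary in the table. This is Version 1.0 with no amendments, so neither statement is superseded text.

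**Step 2: what a within-person difference can estimate.**

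- For sleep outcomes, repeated actigraphy over a participant's stay gives several values per person, so a within-person difference can be formed.
- For length of stay, one HDU admission gives one value per participant. There is no before and after value within that admission.
- The comparator named first is routine HDU patients, who are different people. A within-person difference of means has no term for them, so it cannot estimate how participants differ from them.
- The comparator named second is previous admissions, which the Protocol does not define. If these are the participant's own earlier HDU stays, a within-person contrast exists for those who have such stays and for nobody else. The analysis section does not link its method to this comparator.

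**Step 3: what remains for length of stay.** The analysis section allows description, and the Digital Data paragraph mentions aggregate length-of-stay data. Stays can therefore be tabulated for participants beside routine patients. What the stated method does not give is an estimate of the difference between them.

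**Step 4: whether a claim of a shorter stay could rest on such a table.** Allocation is non-randomised. The Informed Consent Process section defines a meaningful study period as at least two weeks and lets the decision be deferred only until two weeks before expected discharge. The Early Termination section excludes early leavers from the results, including those transferred elsewhere and those who feel that their sleep has improved enough. Entry to the analysed group therefore depends partly on the length of the stay itself, and no matching restriction is stated for routine patients. A side-by-side table can describe stays, but it cannot show that the program shortens them.

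**The case against.** The strongest reply is that the primary outcome can still be identified. The field labelled as primary and the sample size section agree on actigraphic sleep duration. This is a small pilot and feasibility study that aims at description and rough effect estimates, so a loosely worded objective does limited harm. That bears on how much damage results, but it does not remove the contradiction: the objective and the first hypothesis still promise a length-of-stay effect.

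It can also be said that the sentence on effect estimation is visibly garbled and may not be meant as an exhaustive restriction, and that a separate statistical analysis plan may hold the detail. Both are fair. The point is therefore not that length-of-stay analysis detail is missing. It is that the one estimation method the Protocol does state does not match the contrast in its primary objective.

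Three stronger readings are tempting, and the documents do not support them:

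- A reader might infer that no comparison with any control is possible. That goes too far. Descriptive tabulation is allowed, and a contrast with participants' own earlier stays may be possible.
- A reader might infer that two primary endpoints inflate the false-positive rate. The Protocol states no significance level, test or success criterion, so there is no error rate to compute. A second endpoint with no planned estimate is not a second test either.
- A reader might infer that the inconsistency will pass into the trial registry. The table holding the registry-type fields already lists length of stay as secondary, and nothing shows that the wording of the objectives would be used instead.

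**Conclusion.** The point holds in this form. The Protocol ranks HDU length of stay as primary in its objectives and first hypothesis and as secondary in its Administrative Information table, and the sample size section sides with the table. The stated within-person difference of means cannot estimate a difference in length of stay from routine HDU patients. At most it could contrast participants with their own earlier HDU stays, if that is what previous admissions means and only where such stays exist. The Protocol does not say how many participants would have them.

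The size is structural, not numerical: one of the two parts of the primary objective has conflicting status and no effect estimate that matches its first-named control group. The conclusion assumes that the analysis sentence, despite its broken wording, means what it says about within-person measures. The contradiction in rank does not depend on that assumption. The matter should be settled before recruitment, because it determines what the study may conclude about length of stay.

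**What to change.** In Study Objectives:

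- Make change in actigraphic sleep duration the sole primary objective, as the Administrative Information table and the sample size section already have it.
- Move HDU length of stay to the secondary objectives.
- Reword the length-of-stay hypothesis to match that secondary status.

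In the Statistical Analysis Plan section:

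- Apply the within-person difference of means to the sleep outcomes.
- State that length of stay is reported descriptively for participants beside routine HDU patients, with no claim that the program shortens admission.
- Say whether previous admissions means participants' own earlier HDU stays. If it does, describe those alongside, for the participants who have them.

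The cost is a change of wording in the objectives, the hypotheses and the analysis paragraph, and the table records that recruitment has not yet begun. No new data are needed for the comparison with routine patients if the aggregate length-of-stay data already mentioned cover them. The downside is that the Protocol gives up a headline claim of an effect on length of stay, which its stated analysis could not have supported.

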Research has shown that the sleep-wake cycle is strongly linked to the environment (Czeisler et al. 1980; Rea et al. 2008) and disruptions to this cycle may result in sleep disturbances as well as negative cognitive and psychological consequences (Lane & East, 2008). Hospital environments tend to report low lighting levels which may distort the normal circadian sleep-wake rhythms. Bendetti et al. (2001) assessed an inpatient hospital setting over 2 years and reported an average reduction of 3.67 days in admission in those rooms facing east compared to rooms facing the west. The addition of increased outdoor activities and light glasses in the current study increases exposure to light which can assist in stabilising the circadian rhythm.

Moreover, evidence-based interventions such as cognitive behavioural therapy for insomnia (CBT-I) has shown promising results within clinical settings involving patients with schizophrenia, psychosis and patients in acute care (Freeman et al., 2015; Sheaves et al., 2017).

This study has 2 goals. The first goal is a pilot study of an integrated, ward-based behavioural therapy (the Sleep Program) to improve the quality sleep of psychiatric inpatients in order to determine its effect, variance of effect and feasibility. The second is to describe the characteristic of sleep, activity and light exposure of patients in a high dependency psychiatric unit using wrist actigraphy.

Actigraphy

Wrist actigraphy has been used to measure sleep rhythms for over 25 years (Kripke et al., 1978, Mullaney et al., 1980). Actigraphs are watch like devices generally placed on the wrist to record movement. Most are based on weighted activity (accelerometry) counts in a given epoch of time which detect sleep/wake according to threshold values. Activity data is then processed and analysed by computer software programs and specialized algorithms are used to estimate sleep and activity parameters. The analysis utilises algorithms which have been developed, compared and validated since the original use of actigraphs (Cole et al., 1992, Sadeh et al., 1994, Jean-Louis et al., 2001, Tryon, 2005, Kripke et al., 2010). As actigraphic devices have evolved, so too has the number of channels used to collect additional data streams (light, event markers, subjective scores, and off-wrist capacitance). (Ancoli-Israel et al, 2003)

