We foresee the duration of the pilot study of approximately 6 months. Recruitment is on a continuous basis; with approximately 4-6 patients recruited at any given time.

Initial recruitment phase is one week, where patients are identified (see recruitment procedures).

Initial recruitment will be 4-6 patients. The patient is recruited for as long as they are an inpatient at the HDU and discontinued at their discharge (or at their request). Subsequent patients are then recruited in the same process to maintain 4-6 patients at any given time in the program for the duration of the pilot study.

PARTICIPANTS

Inclusion Criteria

1. Males 18+ years.
2. Inpatient in psychiatric Male HDU at PMBC
3. Willingness to give informed written consent and willingness to participate to and comply with the study.
4. Literacy in English.

Exclusion Criteria

1. Current substance dependence.
2. Severe cognitive impairment or thought disorder that does not allow participants to consent or follow treatment instructions.
3. Recent time-zone travel (within last 1 month).

STUDY OUTLINE

Interventions

The intervention is an integrated Sleep Program. It comprises of two main components, thrice weekly group sessions and ward environmental initiatives. The overarching aim is to improve sleep through;

1. **Increase daytime activity**, particularly in the morning if possible, with use of the balcony and outdoor areas. It has the ultimate aim of establishing routine. Many patients in a hospital setting experience a lack of activity. For example, patients may spend a lot of time in bed watching TV or napping throughout the day.
2. **Setting regular rhythms** – enhanced light/dark exposure to stabilize circadian rhythms.
3. **Stimulus control and relaxation** – simple breathing techniques, relaxing music through headphones, relaxation on bean bags
4. Encourage patient-driven management through **psychoeducation**, ongoing sleep quality monitoring and feedback, and driving behavioural change in the ward milieu.

The total duration of a patient’s participation in the Program is flexible. However, we consider a 2-week duration as the minimum dose.

Ward environmental initiatives

A number of initiatives are adopted, these are summarised below. They are specific to the participants of the study. Bean bag and visual cues (ward posters) are made available to the participants in their own rooms; while headphones are pre-existing equipment available to all patients in the HDU.

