	Ward environmental initiatives
Stimulus Control Therapy	
 • Consistent wake time at 7am encouraged by ward staff • Beanbags: an alternate place to sit other than the bed
Sleep Psycho-education	
 • Visual cues regarding specific sleep hygiene strategies around patient room and ward area. • Reinforcement, encouragement and further psychoeducation provided by nursing staff
Increased light exposure (regulating circadian rhythm)	
 • Using available open spaces wherever possible enhanced with early morning Retimer™ blue-green light goggles for those with sleep-phase delay
Relaxation	
 • Calming music during wind down • Quiet space with dim lights and beanbags

Activity Groups

Each participant will be invited to participate in thrice-per-week, 30-minute workshops in the program, which aim to provide psychoeducation about sleep, debriefing and sleep-promotion related

activities. It is also aimed at increasing daytime activity and enforcing a regular circadian rhythm. This is conducted on a repeated weekly cycle as outlined below. These sessions will take place on the outdoor area of the HDU (the balcony) where possible such that participants will receive continuous daylight exposure during these sessions. Each session will take place in mid-morning to lunchtime.

Session 1

Session 1 are on Mondays. They are facilitated by a senior Occupational Therapist and a peer-support worker and is designed to instil a routine of activity (via a Cooking group). Initial consenting and program information will be provided to a patient who is commencing. As well, actigraph watch and sleep diary will be provided to the commencing participant, allowing for ongoing record and feedback of their sleep parameters throughout their time in the program. Qualitative feedback regarding sleep will be collected during these sessions.

Session 2

Second sessions are held on Wednesdays, on the balcony of the HDU. They are facilitated by two psychiatry registrars. Prior to the sessions, participants' actigraph watches are collected and sleep data analysed by the research assistant. A visual representation of sleep duration and activity for each patient will be printed prior to the session and given to the registrars, and printouts are identifiable only by participant IDs.

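### Goal 2 and objective 5 promise a description of HDU patients, but actigraphy is recorded only in selected Sleep Program participants while they are under the Program

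*Protocol*

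**What the plan says.** The Background (Disease Background and Rationale) sets two goals: "The second is to describe the characteristic of sleep, activity and light exposure of patients in a high dependency psychiatric unit". Secondary objective 5 repeats this as "To describe the characteristic of sleep, activity and light exposure of patients in a high dependency psychiatric unit using wrist actigraphy". The administrative table names the condition studied as "Inpatient male HDU psychiatric patients of all diagnoses".

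Watches are handed out in Session 1 of the Activity Groups, where an "actigraph watch and sleep diary will be provided to the commencing participant". The Participant Time Line marks actigraphy, ward initiatives and Program groups at recruitment and weekly, and marks no actigraphy at screening. The comparator in the administrative table is routine patients' "length of stay with and without therapy; previous admissions", which involves no watch.

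Exclusions include "Current substance dependence" and, in the administrative table, patients who are "Severely unwell such that not able to give consent or tolerating participation in group sessions". The first aim under Interventions is more daytime activity, "particularly in the morning if possible, with use of the balcony and outdoor areas". The Early Termination section removes the data of early terminators from results and statistical analyses and keeps them only for discussion.

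**The concern.** The population named in the goal and the population that supplies the data differ in two ways. The wearers are a subset of HDU men, chosen on features connected with how unwell they are. They are also recorded only while receiving a program designed to change what is being described.

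At stake is one of the study's two stated goals. The protocol says that the pilot will mainly describe its sample, and it foresees publication. If the result is written up under the objective's present wording, readers would take it as a description of HDU patients, a population that the study does not observe.

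**Working it through.** The protocol ties no figure to this objective, so there is nothing to reproduce. The check traces who is recorded, when, and under what conditions.

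**Who is recorded.** A man must pass each of these filters:

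| Filter | Place in the protocol |
|---|---|
| English literacy; consent and willingness to comply | Inclusion Criteria |
| No current substance dependence; no severe cognitive impairment or thought disorder that prevents consent or following instructions; no recent time-zone travel | Exclusion Criteria |
| Well enough to tolerate group sessions | Administrative table |
| Capacity, judged by the consultant with team consensus | Capacity |
| Decision at least two weeks before expected discharge, which leaves out short stays | Informed Consent Process |
| Did not terminate early (side-effects, change of mind, sleep felt to be good enough, deterioration, medical admission, transfer) | Early Termination |

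No section provides for actigraphy in a patient who fails a filter or declines.

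**What the Program does to the described quantities.** The Background says that outdoor activity and light glasses in this study add to light exposure. Interventions lists more daytime activity and stronger light/dark exposure as aims. The ward measures add an encouraged 7am wake time, use of open spaces and, for men with sleep-phase delay, morning light goggles. Participants' own sleep and activity printouts are discussed with them each Wednesday.

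**Is there an untreated recording?** By the Summary table of sessions:

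- The watch is issued on Monday, 11:30am to 12pm.
- It is collected for analysis before the Wednesday 11:30am session.
- The longest recording before first feedback is Monday 11:30 to Wednesday 11:30 = 2 × 24 h = 48 h, or two nights.
- For a man at the two-week minimum this is 2 of 14 days: 2/14 = 14%.

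The table labels the first Tuesday as free of active intervention for men on Day 2, and it places morning goggles with men on Day 8. This is the least-treated window. It is not defined as a baseline, it follows the cooking group and preliminary psychoeducation, and ward initiatives are already marked at recruitment. It also covers only men who passed the entry filters.

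**How much time is structured?** The workshops take 3 × 30 min = 1.5 h per week, and 1.5/168 = 0.9% of the week. Wake-time, light and ward measures run outside those hours, including on non-session days.

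**The case against.** The strongest reply is that the protocol nowhere promises natural, untreated or representative behaviour. Participants are HDU patients, eligibility is stated openly, the primary objective is limited to participants, and every consent-based study describes those who consent. This stands to the extent that the fault lies in how the objective is worded and is no evidence of planned misreporting. It does not remove the mismatch. Objective 5 lacks the limit that the primary objective carries, and treatment during recording is a separate matter from consent.

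A second reply is that the Program's grip is loose. Men are invited, the wake time is encouraged, goggles are for some only, headphones are available to every HDU patient, the Friday breakfast is open to the whole ward, and workshops fill 0.9% of the week. This also stands in part: the Program deliberately alters activity and light but does not fix them.

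Two stronger readings are tempting:

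- A reader might infer that reported sleep will be too good because the most unwell are left out, and might put minutes on it. The documents do not support this. They give neither the ineligible share nor a sleep difference. Some rules could work the other way, since short stays are left out and men who leave because they feel their sleep has improved enough are dropped.
- A reader might think that comparing session with non-session days would isolate untreated time. It would not: the summary table itself has stimulus control and morning goggles continuing on a Tuesday.

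Finally, this is the fifth secondary objective of an open-label pilot, with no test or decision attached to it. That limits the consequences. It does not make the description valid for the population named.

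**Conclusion.** The point holds as a mismatch between the stated target and the recorded group. Followed as written, the plan yields a description of selected, consenting men under the Program, after removal of early terminators. It cannot describe HDU patients in general.

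Activity and light should be expected to be higher than without the Program. That direction rests on the Program's stated aims and assumes that it has at least some of its intended effect; the documents give no size. For selection bias in sleep, neither direction nor size can be determined. The only sizes that follow from the documents concern the least-treated window: at most about 48 hours, two nights, 14% of a minimum-length participation.

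**What to change.** 1. Restate goal 2 in the Background and secondary objective 5 as describing *Sleep Program participants during the Program*. This is the essential change.
2. Report the numbers screened, ineligible (by reason) and declining beside the description. Candidates are already identified at team meetings and recruitment rates are already of interest, so a tally is enough.
3. Summarise the first-week recording before the first Wednesday feedback separately from later recordings, and label it as the least-treated window, not as an untreated baseline.
4. State an exception to the Early Termination rule so that recordings made before termination stay in this description, as far as the participant's consent allows.

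The cost is wording, a screening tally and a split of recordings that are already planned. No new participants or devices are needed. The downside is a narrower claim and an early summary that is imprecise because it rests on at most about two nights per man.
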